7.1 General Considerations

The study will recruit at least 70 female and male subjects aged 18-70 of skin seeking non-invasive lipolysis and circumference reduction, in 5 sites.

Treatment area: abdomen

Eligible subjects will be screened. Investigators will screen subjects based on the inclusion/exclusion criteria described below after a written informed consent is signed.

7.2 Subject Withdrawal and Replacement

Subjects enrolled in the study can discontinue their participation at any time for any reason without prejudice or reduction in the quality of their medical care. The investigators or sponsor can terminate a

	Safety and Efficacy of Trim II for Non-invasive Lipolysis and Circumference Reduction of Abdomen.	
	Protocol No: DO609924A SIRB ID: 8659	Rev. Date: Jun 3 2022

subject's participation in this study to protect the subject's health or if the subject fails to follow directions resulting in noncompliance to study procedures. Subjects who withdraw or are terminated from the study may be replaced to ensure that at least 70 subjects have completed the study. Subjects who fail to complete the treatment will be replaced and will not be evaluable.

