6.1 Primary Endpoints

- Efficacy of the Trim II treatment for lipolysis and abdominal circumference reduction.
Evaluation of change in abdomen circumference using tape measurements in cm at the 3 months follow-up visit comparing to baseline.
Success criteria: Statistically significant reduction in abdominal circumference tape measurements at the 3 months follow-up visit compared to baseline.
* The primary effectiveness endpoint will be calculated based on those patients whose weight remains stable during the study period. A subject is defined as having maintained her weight during the treatment period if it remained within $\pm 3\%$ (inclusive) of baseline for the respective period.

 I N M O D E	Safety and Efficacy of Trim II for Non-invasive Lipolysis and Circumference Reduction of Abdomen.	
	Protocol No: DO609924A SIRB ID: 8659	Rev. Date: Jun 3 2022

- Safety of the Trim II treatment for lipolysis and abdominal circumference reduction. The occurrence of adverse events will be followed throughout the whole study. Observation, assessment and recording of potential reactions by the investigator. Evaluations will be done immediately after each treatment and at the follow-up visits. The frequency, severity and causality of reactions will be recorded.

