9.4 Investigator Records

The Investigator will report all Adverse Events which occur with each subject throughout the study and follow-up period and will record them in the CRF Adverse Events Investigation Form. The Investigator will categorize Adverse Events according to:

- Serious or non-serious
- Severity
- Anticipated or unanticipated
- Relationship to device use

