14.1 Analysis Sets

- Safety Analysis Set

The safety analysis set will include all subjects using Embrace procedures at least a single time.

- Performance Analysis Set

Performance analysis set will consist of all subjects providing at least one post treatment performance measurement.

- Treatment of Missing Values

Only observed data will be used; i.e. missing data will not be imputed.

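### Section 7.2 makes subjects who do not complete treatment not evaluable, with no exception for safety, which conflicts with the all-treated safety set in 14.1

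*Combined protocol and SAP*

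**What the plan says.** Section 6.1 lists safety as a primary endpoint beside abdominal circumference: "The occurrence of adverse events will be followed throughout the whole study". Section 9.4 requires recording for everyone: "The Investigator will report all Adverse Events which occur with each subject throughout the study and follow-up period".

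Section 7.2 deals with withdrawal and replacement. The investigators or the sponsor may terminate a "subject's participation in this study to protect the subject's health or if the subject fails to follow directions resulting in noncompliance to study procedures". It continues: "Subjects who withdraw or are terminated from the study may be replaced to ensure that at least 70 subjects have completed the study". The next sentence reads: "Subjects who fail to complete the treatment will be replaced and will not be evaluable".

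Section 14.1 defines the analysis sets. For safety: "The safety analysis set will include all subjects using Embrace procedures at least a single time". For efficacy: "Performance analysis set will consist of all subjects providing at least one post treatment performance measurement". It adds that only observed data are used, without imputation.

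**The concern.** Neither set in 14.1 requires completed treatment, yet 7.2 removes subjects because they did not complete it. The group removed can include subjects stopped to protect their health, and these are the subjects who matter most for a safety endpoint. Anyone whose adverse event ends treatment before the third session is a non-completer by definition.

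The 14.1 sentence that would keep such subjects in the safety set names Embrace. The investigational product is Trim II, and Embrace is not defined. The intended meaning can be inferred, but the population for a primary endpoint should not rest on inference.

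At stake is the reported adverse event rate. If the choice between the two sections stays open until the data are known, the denominator of a primary endpoint in an open-label study could be chosen with the results in view. The rate would be biased downward whenever subjects who stop have more events than completers.

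**Working it through.** **Comparison of the text.** Take a subject who receives the first of three treatments, has an adverse event and is stopped.

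| Question | Section 7.2 | Section 14.1 |
|---|---|---|
| Counted for safety? | Not evaluable; no exception | Yes, one use is enough (product misnamed) |
| Counted for performance? | Not evaluable | Yes, if one post-treatment measurement exists |
| Replaced? | May be (withdrawn or terminated); will be (treatment not completed) | Not addressed |

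No section ranks one rule above the other, and 7.2 does not say which analyses evaluable refers to. Section 9.4 settles what is collected but not who is counted.

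**What can be computed.** The plan gives no power, effect size, standard deviation, dropout rate or event rate, so it contains no figure on this point to reproduce. The only input from the documents is the target of 70 completers. Everything below is illustration under stated assumptions.

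*How many subjects could be affected.* Number treated to reach 70 completers = 70/(1 − d), rounded up. Assume that all who drop out had at least one treatment and did not complete the course.

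- d = 5%: 70/0.95, so 74 treated and 4 non-completers
- d = 10%: 70/0.90, so 78 treated and 8 non-completers
- d = 15%: 70/0.85, so 83 treated and 13 non-completers
- d = 20%: 70/0.80, so 88 treated and 18 non-completers

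*Chance that at least one subject is stopped for an adverse event.* With probability p per subject, this is 1 − (1 − p)^70 among 70 subjects: 51% for p = 1%, 76% for p = 2% and 97% for p = 5%.

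*Effect on a device-related event rate.* Assume 70 completers without such an event and k further subjects stopped for one. Exact (Clopper-Pearson) 95% limits are the 0.025 quantile of Beta(x, n − x + 1), taken as 0 when x = 0, and the 0.975 quantile of Beta(x + 1, n − x).

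| k | If 7.2 governs | If all treated are counted |
|---|---|---|
| 1 | 0/70 = 0% (0 to 5.1%) | 1/71 = 1.4% (0.04 to 7.6%) |
| 3 | 0/70 = 0% (0 to 5.1%) | 3/73 = 4.1% (0.9 to 11.5%) |
| 5 | 0/70 = 0% (0 to 5.1%) | 5/75 = 6.7% (2.2 to 14.9%) |

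The middle column does not change with k. That is the structural point.

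*Effect on the rate of any adverse event.* Assume 5/70 = 7.1% among completers and 10 subjects who stop. The all-treated rate is (5 + 0)/80 = 6.3%, (5 + 2)/80 = 8.8% or (5 + 5)/80 = 12.5% with 0, 2 or 5 events among those who stop. The direction depends on how the two groups compare. There is no bias if their rates are equal.

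**Primary circumference test.** The effect here is limited. A subject who stops and has no 3-month value is already outside a paired t-test on observed data. Section 7.2 changes that test only for subjects who stop but still supply the 3-month measurement.

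**The case against.** The best defence is that 7.2 is a recruitment rule. On that reading, non-completers do not count towards the 70, evaluable means evaluable for efficacy, and 14.1, the only section that defines analysis sets, decides who is analysed for safety. The reading is plausible, but it is not written down. It also leaves 7.2 in conflict with the 14.1 performance set, which admits a non-completer with one post-treatment measurement.

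Termination to protect health appears in a different sentence from the not-evaluable clause, and terminated subjects are described only as replaceable. This narrows the point without removing it, because a subject terminated before the third treatment falls under both sentences.

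Several further points stand:

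- No adverse event data are lost, since 9.4 and 9.5 require recording and reporting for all subjects.
- The safety endpoint has no success criterion or test, so no formal decision turns on the denominator.
- Embrace is probably an editorial slip. Its absence elsewhere can be checked only in the available text, parts of which are blacked out or removed.
- The figures above show what is possible. They do not estimate what will happen.
- Deleting the clause would let a weight-stable subject who stops but returns at 3 months enter the primary efficacy test. That is what the 14.1 performance set already provides.

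**Conclusion.** The concern holds and should be fixed. The two sections give different answers for the same treated subject, and nothing in the plan resolves the difference. If 7.2 is followed as written, subjects stopped for an adverse event drop out of the primary safety result. If 14.1 is followed, they do not.

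The loss is therefore a risk that depends on which section is applied, and its size is unknown. In the illustrations, a true count of 1 to 5 treatment-ending events (1.4% to 6.7% of those treated) would be reported as 0/70. These figures assume no device-related event among completers and full replacement to 70. The conflict in the wording is certain; the amount of bias is not.

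**What to change.** **Section 14.1.** Define the safety set as all subjects who received at least one full or partial Trim II treatment, including those later withdrawn, terminated or replaced. Name it as the population for the primary safety endpoint. This also removes the reference to Embrace.

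**Section 7.2.** Delete the clause that makes non-completers not evaluable. State that replaced subjects stay in the safety set and, where they meet the 14.1 rule, in the performance set. Reconcile the two replacement sentences, one of which is optional and the other mandatory. Replacement can remain as a recruitment rule to reach 70 completers.

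**Cost.** Wording in two sections, settled before the data are known. No new data, visits or change of test are needed. The reported adverse event rate may be slightly less favourable, and a few subjects who stopped early but have a 3-month measurement may enter the circumference analysis.

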7.3 Subject Identification

A unique subject identification code will be assigned when an individual subject is qualified for enrolment.

Subject identification details will be coded using subject's initials, site number and subject case number. Subject initials will be composed of the first letter of given name, first letter of middle name and first letter of family name (for example, ADS for Adam Daniel Smith) and a three-digit sequential number. The investigator will complete subject identification on a confidential site log, which will be used for the purposes of traceability.

An example is provided below:

ADS 101

In any case, other identification details (i.e. full names, phone numbers, etc,) will not be filled in any way in the Case Report Files. The identification log will be kept in the study file only.

7.4 Inclusion Criteria

- Female and male subjects, aged 18-70.
- BMI ≤ 30.
- Subjects seeking non-invasive lipolysis and circumference reduction of abdomen
- Female should not be pregnant or lactating and must be either post-menopausal, surgically sterilized, or using a medically acceptable form of birth control at least 3 months prior to enrolment (i.e., oral contraceptives, contraceptive implant, barrier methods with spermicide or abstinence).
- In addition, negative urine pregnancy test as tested before each treatment and at the last visit for women with childbearing potential (e.g. not menopause).
- General good health confirmed by medical history and skin examination of the treated area.
- The subjects should understand the information provided about the investigative nature of the treatment, possible benefits and side effects, and sign the Informed Consent Form, including permission to use photography.
- The subjects should be willing to comply with the study procedure and schedule, including the follow up visits, and will refrain from using any other abdominal treatment methods during the entire study period.

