Safety and Efficacy of Trim II for Non- invasive Lipolysis and Circumference Reduction of Abdomen

NCT05398159

Last Updated Jun 3 2022

I N M O D E

Safety and Efficacy of Trim II for Non-invasive Lipolysis and Circumference Reduction of Abdomen.

Protocol No: DO609924A SIRB ID: 8659

Rev. Date: Jun 3 2022

Study Name: Safety and Efficacy of Trim II for Non-invasive Lipolysis and Circumference Reduction of Abdomen.

Protocol No.: DO609924A

Sponsor: InMode Ltd.
[name]
[name]
[name]
[contact]

I N M O D E

Safety and Efficacy of Trim II for Non-invasive Lipolysis and Circumference Reduction of Abdomen.

[figure not shown]
Protocol No: DO609924A SIRB ID: 8659

Rev. Date: Jun 3 2022

Approvals:

Revision Log:

Revision #	Date	Modification
A	January 2021	First Release
B	June 2022	

I N M O D E

Safety and Efficacy of Trim II for Non-invasive Lipolysis and Circumference Reduction of Abdomen.

Protocol No: DO609924A SIRB ID: 8659

Rev. Date: Jun 3 2022

1. Protocol Synopsis

Study Title	Safety and Efficacy of Trim II for Non-invasive Lipolysis and Circumference Reduction of Abdomen.
Protocol No	DO609924A
Sponsor	InMode Ltd.
Investigational Product	Trim II hands free device.
Study Design	Prospective, open label clinical study.
Principle Investigator and Study Site	Site 01: Site 02: Site 03: Site 04: Site 05:
Patient Population and Sample Size	At least 70 female and male subjects, from 5 investigational sites, aged 18-70 seeking non-invasive lipolysis and circumference reduction of abdomen will be enrolled.
Study Duration	Eligible subjects will receive 3 bi-weekly treatments (once in 2 weeks) with Trim II hands-free applicator belt according to the study protocol. Trim II hands-free applicator composed of 4 units applied to the abdominal area, using a single-use belt. Each treatment duration will be 45-60 minutes. Study duration for each subject is approximately 6 months (including screening, 3 treatments and 2 follow-up visits at 1 and 3 months post last treatment). Histological samples will be taken from treated area of 8-10 subjects (in total) at baseline and at 3 months follow-up visit. Overall study duration will be approximately 12 months, depending on the subject recruitment rate.

I N M O D E

Safety and Efficacy of Trim II for Non-invasive Lipolysis and Circumference Reduction of Abdomen.

Protocol No: DO609924A SIRB ID: 8659

Rev. Date: Jun 3 2022

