7.5 Exclusion criteria

- Active electrical implant/device in any region of the body, including pacemaker or internal defibrillator
- Permanent implant in the treated area such as metal plates, screws or silicon, metal piercing or other.

I N M O D E

Safety and Efficacy of Trim II for Non-invasive Lipolysis and Circumference Reduction of Abdomen.

Protocol No: DO609924A SIRB ID: 8659

Rev. Date: Jun 3 2022

- Current or history of skin cancer, or current condition of any other type of cancer, or pre-malignant moles.
- Severe concurrent conditions, such as cardiac disorders, sensory disturbances, epilepsy, uncontrolled hypertension, and liver or kidney diseases.
- History of skin disorders, keloids, abnormal wound healing, as well as very dry and fragile skin.
- History of bleeding coagulopathies or use of anticoagulants except for low-dose aspirin.
- Patients with history of diseases stimulated by heat, such as recurrent Herpes Simplex in the treatment area, may be treated only following a prophylactic regimen.
- Impaired immune system due to immunosuppressive diseases such as AIDS and HIV or use of immunosuppressive medications.
- Pregnancy and nursing.
- Poorly controlled endocrine disorders, such as Diabetes, or thyroid dysfunction and hormonal virilization.
- Isotretinoin (Accutane) within last 6 months.
- Any active condition in the treatment area, such as sores, Psoriasis, eczema, and rash, open lacerations, abrasions or lesions, infection in the area to be treated.
- Any surgical procedure in the treatment area within the last 12 months or before complete healing.
- Having received treatment with light, laser, RF, or other devices in the treated area within 2-3 weeks for non-ablative procedures, and 6-12 weeks for ablative fractional laser resurfacing (according to treatment severity) prior to treatment, except special recommendations.
- Use of non-steroidal anti-inflammatory drugs (NSAIDS, e.g., ibuprofen-containing agents) one week before and after each treatment session, as per the practitioner's discretion.
- As per the practitioner's discretion, refrain from treating any condition which might make it unsafe for the patient
- Participated in another investigational drug or device study or have completed the follow-up phase for any previous study less than 30 days prior to the first evaluation in this study.

8. Study Procedures

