14.2 Statistical Analysis

[figure not shown]
Means, and standard deviations for each characteristic will be calculated. Paired sample t-test will be computed to assess changes in before treatment and follow-up scores. Statistical significance will be calculated and two-tail significance level of 0.05 will be used.

15. Data Management Plan

Case Report Forms and questionnaires will be retrieved by Monitors after source data verification and resolution of monitoring queries. Documents will be delivered to InMode Ltd onsite data management facility where forms will be logged in, and then data will be entered using a double entry method.

16. References

4. [name], [name] Neuromascular Electrical Stimulation and Strength Recovery

I N M O D E

Safety and Efficacy of Trim II for Non-invasive Lipolysis and Circumference Reduction of Abdomen.

Protocol No: DO609924A SIRB ID: 8659

Rev. Date: Jun 3 2022

of Postnatal Diastasis Recti Abdominis Muscles. Ann Rehabil Med 2017;41(3):465-474 pISSN: 2234-0645 • eISSN: 2234-0653

17. Investigator Study Acknowledgment

Investigator’s Statement:

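### Eligibility does not address recent weight stability, diet, exercise or weight-loss drugs, so net lifestyle weight loss inside the ±3% band of section 6.1 is counted as device effect

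*Combined protocol and SAP*

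**What the plan says.** The synopsis describes a "Prospective, open label clinical study" with no control arm, enrolling "At least 70 female and male subjects, from 5 investigational sites". Section 6.1 sets the rule for efficacy: "Success criteria: Statistically significant reduction in abdominal circumference tape measurements at the 3 months follow-up visit compared to baseline". No minimum reduction in cm is required. The same section adds: "The primary effectiveness endpoint will be calculated based on those patients whose weight remains stable during the study period", and defines stable as within ±3% of baseline, inclusive.

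Section 14.2 gives the test: "Paired sample t-test will be computed to assess changes in before treatment and follow-up scores", and a "two-tail significance level of 0.05 will be used". No covariate is named.

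The eligibility lists in the synopsis and in 7.4 and 7.5 match on this point. The nearest inclusion item is that subjects "will refrain from using any other abdominal treatment methods during the entire study period". The nearest medical exclusion is "Poorly controlled endocrine disorders, such as Diabetes, or thyroid dysfunction and hormonal virilization", which concerns uncontrolled disease and not attempts to lose weight. Section 8.1 records medicines taken in the 6 months before screening. Appendix 1.0 schedules concomitant medication at every visit, and weight at screening, at the second and third treatments and at both follow-ups. No diet or exercise data are scheduled.

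**The concern.** The plan accepts that weight change can move the tape measurement, because it removes subjects whose weight moved too far. That rule acts only at analysis, and it filters without adjusting: a subject who loses 2.9% stays in with the full tape reduction, and one who loses 3.1% leaves after three treatments. Nothing at entry lowers the chance of weight loss during follow-up. A subject who started a diet, a training programme or a weight-loss drug the week before screening is eligible, and five sites have no common text to apply.

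The population is people seeking abdominal reduction, and the primary visit is 90 days after the third treatment, about four months after the first. A modest average downward drift is plausible. With no control arm it cannot be separated from a device effect, and with no minimum cm a small shift can be enough. The risk is a primary efficacy claim that partly reflects lifestyle change.

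**Working it through.** The plan gives no power, effect size or SD, so there is no figure of its own to reproduce. The check asks how often the success rule is met with zero device effect when enrolled subjects lose a little weight on average and the ±3% filter is applied.

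**From the documents:** 70 subjects; paired t-test, two-sided 0.05; success in the direction of reduction; only subjects within ±3% analysed.

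**Assumed (not in the documents):** 75 kg, so 1% = 0.75 kg; 0.5-1 cm of girth per kg; total SD of circumference change among enrolled subjects 2-4 cm; weight change normal with mean -1% and SD 1%, 2% or 3%.

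**Step 1, the filter.** With mean μ and SD s, let a = (-3 - μ)/s and b = (3 - μ)/s. The share kept is Φ(b) - Φ(a). The mean kept is μ + s[φ(a) - φ(b)]/[Φ(b) - Φ(a)]. For s = 2, a = -1 and b = 2:
- Share kept = 0.9772 - 0.1587 = 0.8186, and 70 × 0.8186 = 57.3 subjects.
- Mean kept = -1 + 2 × (0.2420 - 0.0540)/0.8186 = -0.54%.
- Girth shift = 0.54 × 0.75 kg × 0.5-1 cm per kg = 0.20-0.41 cm.

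The same formulas give 68.4 kept with mean -0.94% for s = 1, and 45.9 kept with mean -0.29% for s = 3.

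**Step 2, the threshold.** The smallest significant mean reduction is t(0.975, n-1) × SD/√n. At n = 57, 2.003 × SD/√57 = 0.53, 0.80 and 1.06 cm for SD 2, 3 and 4. The 0.20-0.41 cm shift lies below all three, so at s = 2 drift alone usually fails but succeeds more often than the nominal rate.

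**Step 3, chance of success**, by simulation with the filter applied (ends move by about 0.01 between runs). Within each cell the range runs from 0.5 to 1 cm per kg.

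| SD of weight change | Kept of 70 | Total SD 2 cm | SD 3 cm | SD 4 cm |
|---|---|---|---|---|
| 1% | 68 | 0.30-0.82 | 0.16-0.49 | 0.10-0.31 |
| 2% | 57 | 0.12-0.43 | 0.08-0.18 | 0.06-0.12 |
| 3% | 46 | 0.06-0.23 | 0.04-0.10 | 0.04-0.06 |

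With no average drift, success is about 0.025 in every setting, the nominal rate in one direction.

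**Step 4, check of the 0.43.** At s = 2, 1 cm per kg and total SD 2, weight contributes SD 2 × 0.75 = 1.5 cm, so the residual variance is 4 - 2.25 = 1.75. The filter cuts the SD of weight change to 1.44%, or 1.08 cm. The SD among kept subjects is √(1.75 + 1.08²) = 1.71 cm. The noncentrality is 0.406/1.71 × √57.3 = 1.80, and the noncentral t gives 0.42. If 2 cm is taken as the SD among kept subjects instead, the result is about 0.33.

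**Step 5, a limit on the 0.23.** At s = 3, 1 cm per kg and total SD 2, weight alone would contribute 3 × 0.75 = 2.25 cm, more than the assumed total. The 0.23 is reached only by setting the residual to zero, so it is an outer bound. The other combinations in that row reach about 0.10.

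**The case against.** Several points on the other side are fair.

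- **The plan has a safeguard, and it works in part.** A reader might take all 70 subjects with an average loss of 1% (0.375-0.75 cm) and compute a chance of success of 0.34-0.87 at SD 2, 0.18-0.54 at SD 3 and 0.12-0.34 at SD 4. That omits the section 6.1 filter, which lowers both the number kept and the mean loss among them. Those figures need 1% to be the mean among analysed subjects with none removed.
- **The width of the band proves little.** A reader might note that 3% of 75 kg is 2.25 kg, or 1.1-2.25 cm, and that this exceeds the 0.48-0.95 cm needed for significance at n = 70. That sets one subject's maximum against a group mean, and would matter only if nearly everyone sat at the lower edge.
- **The bias has no fixed direction.** The band is symmetric, and in-band gain works against success. The concern needs net loss.
- **Section 6.1 does not assume stability.** It restricts the analysis to subjects measured as stable.
- **Some information is collected.** Weight-loss drugs would appear in the medication records, and the commitment on other abdominal treatments could be stretched to abdominal training. Neither is a rule on drugs, diet or general exercise.
- **An entry pledge is self-reported.** It cannot remove loss inside the band. The deeper causes are the single arm, the lack of a minimum cm and the unadjusted test.

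These points reduce the size and shape the remedy. They do not close the gap in the eligibility lists.

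**Conclusion.** The gap holds: no eligibility text addresses recent weight stability, diet, exercise or weight-loss drugs, and the analysis credits any net in-band loss to the device. With an enrolled mean change of -1% and no device effect, the chance of success is about 0.06-0.43 (weight-change SD 2%), 0.10-0.82 (SD 1%) or 0.04-0.23 (SD 3%, where 0.23 is an outer bound), against 0.025. These figures depend entirely on the assumed body weight, cm per kg, SDs and drift.

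A reader might infer that lifestyle change would by itself deliver success. The documents do not support that: they give no evidence of drift, and in most of the range drift alone fails more often than it succeeds. A reader might also infer that the missing screen explains the loss of completers. At SD 2%, about 13 of 70 leave with a -1% drift, but about 9 leave with none, and section 7.2 does not provide for replacing completers lost to the weight rule. The added loss is small. This is worth correcting because the remedy is cheap. It does not invalidate the design on its own.

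**What to change.** - **7.4 and synopsis:** add that weight has been stable before screening (for example self-reported within ±3% over 3 months; the look-back is the sponsor's choice) and that the subject agrees to keep usual diet and exercise unchanged until the 3-month visit.
- **7.5 and synopsis:** exclude current, recent or planned use of weight-loss medication, or of a structured weight-loss or abdominal training programme.
- **Section 8 and Appendix 1.0:** ask one diet and exercise question at each visit, beside the concomitant-medication review.
- **14.2:** keep the section 6.1 rule and add a sensitivity analysis of circumference change adjusted for weight change. One form is to regress change in cm on percentage weight change and report the estimate at zero weight change. It uses weights already recorded and addresses the in-band loss that a pledge cannot prevent. It will not capture exercise that alters girth without altering weight, which is why the visit question is also needed.

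The cost is a few more screen failures, one extra CRF item and one further analysis.
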